3.2. Endpoints

The following two sub-chapters list the primary and secondary endpoints to be analyzed together with their definition. For more information, as well as underlying ICP, OPS and ATC codes, see Chapter 3.1.

3.2.1. Primary Endpoints

Variable	Definition
Revision	
 - Time from surgery to revision defined above.
Implant removal (only)	
 - Time from surgery to implant removal - Within first 3 months after surgery, an implant removal will also be considered as a surgical complication - No SC is allowed to occur within 3 months and on the same day
Surgical complications (SC)	
 - Time from surgery of OF to surgical complications, with death being considered as a competing risk event.
In-hospital SC rate (IH-SC)	
 - SC after surgery during index hospitalization (yes/no)
In-hospital implant-associated complications (IH-IAC)	
 - IAC after surgery during index hospitalization
In-hospital non-implant associated complications (IH-non-IAC)	
 - Non-IAC after surgery during index hospitalization

Table 3: Primary endpoints

3.3. Possible sources of bias due to variable definition

In-hospital complications will be defined by the above reported codes that are coded in the same inpatient case as the surgery of OF (i.e. the index case series). For all OPS codes, the date has to be later in course of hospitalization than the surgery of OF (datum surgery with LPF/TBW < datum OPS code). ICD codes are all coded at the date of discharge and no chronological order within one case will be available. However, the defined complications are of such a serious nature that they always represent an unfavorable scenario from the patient's point of view, irrespective of the chronological course during hospitalization. It can also be assumed that, preoperatively, they did not represent a contraindication for surgery, if they were present before. Thus, it can be firstly assumed that complications predominantly occurred after surgery and, secondly, that any bias from (a few) events happens before surgery should be very low. In summary, all ICD codes for the above-mentioned complications that will be coded during the index case will be considered as in-hospital complications.

For all SC, only OPS ipsilateral coded procedures will be considered as complications. For ICD codes, no laterality will be available and thus, SC during follow-up will be mostly defined on OPS codes. For

osteonecrosis, however, it is therefore possible to wrongly count contralateral events as a complication which might add some bias, but both groups will be effected in the same manner.

4. Statistical Methods

4.1. Descriptive Statistics of Baseline Variables and Treatment trends

For descriptive analysis of treatment trends over time and baseline characteristics, the entire cohort will be used. For nominal and ordinal variables, the absolute and relative numbers will be calculated. All baseline parameter (see table 2 in chapter 3.1) will be reported for the entire cohort and grouped by treatment groups.

Time trends in the treatment of olecranon fractures using TBW vs LPF over study time will be presented as absolute and relative frequencies per year and possible trend will be tested via two-sided Cochran-Armitage trend test. Subgroup analyses, i.e. female/male patients or grouped by age, will be performed, if the data will be sufficiently large. All calculated p-values for time trends will be only calculated to illustrate the results and are in no way of a confirmatory nature. Therefore, the p-values in this part should be interpreted with caution.

4.2. Analysis of Primary and Secondary Endpoints

To analyze differences in the treatment groups (TBW versus LPF), a 1:1 propensity score (PS) matching will be performed to guarantee sufficient balance between them. Each patient treated with TBW will be matched with a patients treated with LPF, based on age, sex, fracture complexity, year of treatment, all clinical relevant comorbidities and pharmaceutical therapy at index hospitalization (listed in table 2 “Comorbidities at Baseline” and “Pharmaceutical therapy”). Analysis set will defined by all patients included in the matching.

The balance will be evaluated using risk differences, z-differences and sum of squared z-differences (SSQZ) and will be reported for all variables before and after matching. The hyper-parameter (i.e. caliper with, distance for continuous variables, factors with exact matching) of the PS matching will be chosen in such way that the sum of squared z-differences (SSQZ) will be minimized around the number of variables included in the matching procedure (k), i.e.

$$k/2 \leq SSQZ \approx k.$$

Overlap between matching groups will be presented by the histogram of $logit(p_s)$. The dependency of the Matching partners and thus a stratified evaluation will not be considered.

In-hospital complications and 30-days mortality

All in-hospital endpoints as well as 30-day mortality are given by binary variables. Absolute and relative frequencies for both treatment group will be reported and differences between them will be tested via two-sided χ^2 -independence test. Moreover, a multivariable logistic regression model will be performed to adjust for patient's risk profile. Odds ratio (OR) comparing TBW and LPF for all in-hospital complications and 30-day mortality will be illustrated using forest plots.

30-day mortality will be defined as primary endpoint instead of in-hospital death to avoid bias due to differences in the LOS of both treatment groups. Absolute and relative frequencies for in-hospital death will be reported for the sake of completeness; however, p-values for possible differences will not be interpreted in a confirmatory manner.

Complications during follow-up

The start of observation will be defined by the day of surgery. Median follow-up time will be determined for the entire analysis set using Kaplan Meier estimate (death as censored event).

For **OS, MAE and TE**, the Kaplan-Meier estimator will be determined for both groups and plotted for the survival functions along with unadjusted 95% confidence intervals (95%CI). Furthermore, at different time points (1 month, 3 months, 1-5 years), the event rates (1- survival function) will be reported with 95%CI and the total number of observed events per group. For the comparison of groups, the Log rank test will be conducted. Multivariable Cox regression models will analyze the impact of baseline variables on the endpoints. The resulting hazard ratios (HRs) will be presented along with its unadjusted 95% confidence intervals and illustrated in forest plots.

For **SC and minor outpatient complications**, death will be considered as a competing risk event. Hence, cumulative incidence function (CIF) determined by Aalen-Johansen estimate and sub-distributional hazards using Fine & Gray Cox models² will be calculated. Groups will be compared with Gray's test. All results were presented in an analog way explain above (plot of CIFs, reporting of CIF at different time points, forest plot for the HRs).

Multiple comparison problem

As mentioned above, patients were grouped by age (i.e. 18-44 years, 45 – 69 years, ≥ 70 years), where younger (<70 years) and older patients (≥ 70 years) will be analyzed (and published) in separate studies. To account for the multiple test problem in each study separately (<70 years and ≥ 70 years), all p-values comparing treatment-effects determined from multivariable analysis of all primary endpoint will be jointly adjusted using Bonferroni-Holm method³ to control the family-wise error rate with respect to the multiple comparison problem. Adjusted p-values will be compared with the overall significance level of 5%.

Time-dependent analysis

Should the evaluation reveal an overlap of the survival curves approximated with Kaplan-Meier, we will further investigate these with a time-dependent survival analysis or landmark analysis with suitably chosen cut-off values. In addition, the time-dependent hazard ratio will be plotted in the form of a step function. All time-dependent analyses will be of an exploratory nature only.

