The incidence of the olecranon fracture (OF) in adults is around 12 per 100,000 inhabitants per year.¹ The anatomical shape of the proximal ulna is largely responsible for the stabilization of the humeroulnar joint and reconstruction is therefore obligatory, but often challenging. Surgical treatment of the olecranon fracture is performed using tension band wiring (TBW) or locking plate fixation (LPF) osteosynthesis. It is not yet clear, which procedure is superior for a specific patient. In future, an individualized and objectified assessment of expected general and fracture-specific complications should enable the treatment to be individually adapted to the patient's risk profile. This shall prevent complications, unnecessary treatments, and treatment costs. In the project presented here, the reality of care for surgically treated patients with olecranon fractures will be analyzed using routine data collected by the BARMER health insurance fund.

The aim of the study is to analyze differences in the outcome of patients with an olecranon fracture treated with TBW compared to LPF and to identify independent risk factors for unfavorable course.

2. Population

The German reimbursement system governs the remuneration of health care services subject to encoded diagnoses (International Statistical Classification of Diseases, German Modification; ICD-10 GM) and procedures (German procedure classification – *Operationen- und Prozedurenschlüssel*; OPS) by means of the 'German Diagnosis Related Groups' taxonomy (GDRG). This obligatory documentation and accounting system is specified and further regulated in detail by mandatory coding instructions.

The database consists of retrospective health claims data of the German BARMER health insurance company. This includes anonymized data from following sectors:

- Inpatient data (§301 SGB V): In addition to information on costs, duration of hospitalization and information about treating hospital, standardized information on diagnoses (coded according to ICD-10 GM) and procedures (coded according to OPS) are available.
- Outpatient data (§295 SGB V): In addition to information on costs, diagnoses (ICD-10 GM) and procedures (OPS).
- Pharmaceutical therapies (§300 SGB V): Information on medication (coded via ATC classification), as well as costs and DDD (Defined Daily Dose).

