2.2. Inclusion and Exclusion Criteria

Within an index period from 01/2011 to 09/2023 all patients will be included, who met all inclusion criteria and no exclusion criterion (see table 1).

Inclusion Criteria
Inpatient coded diagnosis of olecranon fracture (ICD S52.01)
Exclusion Criteria
Incomplete basic information
Incomplete insurance status within two years before index
Previous treatment of olecranon fracture
Unclear treatment of olecranon fracture (other as variable and code from table 2)
Age < 18 years
Coded polytrauma
Bone tumors/ bone metastasis
Both sides injured or missing information of surgery side

Table 1: Inclusion and exclusion criteria.

The first hospitalization within the index period with coded diagnosis for OF (S52.01 main and secondary diagnosis) and at least one coded surgical treatment using TBW (OPS 5-793.27, 5-794.17) or LPF (OPS 5-793.k7, 5-794.k7) will be defined as the index case. In addition, all overlapping cases without time delay (admission date new case = discharge cases with surgery) will be defined as one case-series and will be included in the index case.

3. Endpoints and Variables

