3.1. Variables

The following table lists all variables relevant to the analysis along with their ICD, OPS or ATC codes. For each patient, possible comorbidities will be recorded at baseline by including all outpatient and inpatient information coded within two years prior to the index hospitalization and during first hospitalization (exceptions are marked accordingly).

The "minor outpatient complications" defined below (see the last row of the following table) will be based exclusively on outpatient information coded after discharge of the first hospitalization.

All other variables concerning complications during follow-up will be collected exclusively from inpatient information during hospitalization and after discharge.

Variable	Classification	Code
Olecranon fracture	ICD	S52.01
Simple fracture TBW	OPS	5-793.27
Multi-fragmented TBW	OPS	5-794.17
Simple fracture LPF	OPS	5-793.k7
Multi-fragmented LPF	OPS	5-794.k7
Comorbidities at Baseline		
Alcohol abuses	ICD	E24.4, F10, G31.2, G62.1, G72.1, I42.6, K29.2, K70, K85.2, K86.0, T51.0, T51.9
Arthrosis	ICD	M15-M19 (only before index admission)
Atherosclerosis	ICD	I70
Atrial fibrillation and flutter	ICD	I48
Asthma		J45
Bone tumor/metastasis	ICD	C40.0, C79.5, C79.86, C79.9
Cancer	ICD	C
Chronic kidney disease	ICD	N18, N19
Chronic polyarthritis	ICD	M05, M06
Congestive heart failure	ICD	I50
Coronary heart disease	ICD	I25
Dementia	ICD	F00, F01, F02, F05.1, G30, G31.1
Depressive episode	ICD	F32, F33
Diabetes mellitus	ICD	E10-E14
Dorsalgia	ICD	M54
Hypertension	ICD	I10-I15
Infection	ICD	M86.02, M86.12, M86.22, M86.32, M86.42, M86.52, M86.62, M86.82, M86.92, T84.5, T84.6, T84.7 (only before index admission)
Neurotic, stress-related and somatoform disorders	ICD	F41, F43, F45
Nicotine abuses	ICD	F17
Obesity	ICD	E66
Osteoporosis	ICD	M80-M85
Parkinson	ICD	G20
Polytrauma	ICD, OPS, DRG	ICD: T07 , OPS: 5-982 , or coded DRG started with "W" (only during index hospitalization)
Elbow arthrosis	ICD	M25.52 (only before index admission)
Previous stroke	ICD	I60-I69 (only before index admission)
Prior level of care (LoC)		Level of care in the database (from 2017)
Problems related to care-provider dependency	ICD	Z74

Pharmaceutical therapy		
Any anticoagulant	ATC	B01AA, B01AB, B01AC, B01AE, B01AF, B01AX
Vitamin D or calcium	ATC	A11CC
Bisphosphonates	ATC	M05BA, M05BB
Any osteoporosis pharmacotherapy	ATC	Vitamin D/Calcium or Bisphosphonates
Contraceptives for topical use	ATC	G02B (only for matching)

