Implant removal (TBW)	OPS	5-787.07, 5-787.17, 5-787.27, 5-787.67, 5-787.77, 5-787.g7, 5-810.34, 5-810.35
Revision of the osteosynthesis (LPF and TBW)	OPS	5-785.07, 5-785.17, 5-785.27, 5-785.37, 5-785.47, 5-785.57, 5-785.67, 5-785.77, 5-789.37, 5-78a.07, 5-78a.17, 5-78a.27, 5-78a.57, 5-78a.67, 5-78a.77, 5-78a.87, 5-78a.97, 5-78a.c7, 5-78a.g7, 5-78a.k7, 5-78a.m7, 5-78a.n7, 5-78a.x7, 5-793.07, 5-793.17, 5-793.27, 5-793.37, 5-793.67, 5-793.77, 5-793.87, 5-793.97, 5-793.a7, 5-793.b7, 5-793.c7, 5-793.g7, 5-793.h7,

		5-793.k7, 5-793.m7, 5-793.n7, 5-793.x7, 5-794.07 , 5-794.17, 5-794.27, 5-794.57, 5-794.67, 5-794.77, 5-794.87, 5-794.a7, 5-794.b7, 5-794.c7, 5-794.g7, 5-794.h7, 5-794.k7, 5-794.m7, 5-794.n7, 5-794.x7, 5-824.4 , 5-824.5, 5-825.01 , 5-825.4, 5-825.a, 5-825.m
Resection arthroplasty (for spacer placement)	OPS	5-829.4
Secondary arthroplasty	OPS	5-824.4 , 5-824.5
Arthrolysis	OPS	5-800.64 , 5-800.65, 5-810.24 , 5-810.25, 5-810.94, 5-810.95
Classification of complications and long-term endpoints/events		
Major adverse event		resuscitation, cardiac arrest, myocardial infarction, stroke, acute renal failure, acute liver failure, acute respiratory distress syndrome, sepsis or death from any case
Thromboembolic event		Deep vein thrombosis, pulmonary embolism, ischemic stroke or death from any case
Surgical complications		Adhesive capsulitis, arthrolysis, debridement, frozen elbow, implant removal within first 3 months, infection, infection with antibiotic-resistant germs, joint damage/cartilage damage, luxation, delayed union, non-union/pseudoarthrosis, malunion, nerve injury, vascular injury, osteonecrosis, postoperative stiffness, secondary arthroplasty, secondary arthroscopy, secondary surgery (open) including revision surgery, upper limb amputation
Implant-associated complications (IAC)		Impingement, bursitis, mechanical malfunction or material failure/loosening, periprosthetic or periimplant fracture
Non-implant associated complications (non-IAC)		Infection, infection with antibiotic-resistant germs, hematoma after surgery

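### The propensity score has no variable for open fracture or associated elbow injury, leaving potential residual confounding by injury severity of unknown size and direction

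*Combined protocol and SAP*

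**What the plan says.** Section 4.2 plans 1:1 propensity score matching "based on age, sex, fracture complexity, year of treatment, all clinical relevant comorbidities and pharmaceutical therapy at index hospitalization". The comorbidity and drug covariates come from the Table 2 blocks "Comorbidities at Baseline” and “Pharmaceutical therapy". These blocks list chronic conditions, care dependency and medication. Their one trauma item is polytrauma.

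Table 1 (Section 2.2) has two exclusions that concern the injury: "Coded polytrauma" and "Both sides injured or missing information of surgery side". A further one, "Unclear treatment of olecranon fracture (other as variable and code from table 2", is ambiguously worded. Section 2.2 accepts S52.01 as either a main or a secondary diagnosis, so another injury may be the main reason for admission.

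For binary endpoints, Section 4.2 adds a logistic model adjusting for the patient's risk profile. For time-to-event endpoints it uses Cox or Fine and Gray models with baseline variables. Section 4.3 adds an unweighted full-cohort analysis and three weightings built on a propensity score, for which no separate covariate list is given.

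The surgical complication (SC) composite in Table 2 includes infection, joint damage, luxation, nerve and vascular injury, secondary arthroscopy and "secondary surgery (open) including revision surgery". On inpatient data, Section 2 notes that "standardized information on diagnoses (coded according to ICD-10 GM) and procedures (coded according to OPS) are available".

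**The concern.** The comparison is non-randomised, so its validity rests on the covariate list. Fracture complexity describes how far the olecranon is fragmented. It does not describe the soft tissue or the rest of the elbow. Several SC components are events that a more severe injury could plausibly produce whatever implant was used.

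If such injuries go more often to one implant, and the imbalance survives matching on the listed variables, part of their worse course would be credited to that implant. The comparisons most exposed are SC, revision and the in-hospital complication endpoints. These are primary endpoints under Table 3 and enter the Bonferroni-Holm procedure, which controls multiplicity and does nothing about bias. The planned balance checks (z-differences and their sum of squares) cover only the variables included, so they can look satisfactory while injury severity differs between groups.

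The study's second aim, to identify independent risk factors for an unfavourable course, would also be pursued without these candidate risk factors.

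**Working it through.** The plan states no figure on this point, so there is none to reproduce. The check has two parts.

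**1. Is injury severity handled anywhere?**

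- Eligibility (Table 1): coded polytrauma and bilateral injury are excluded. Nothing names open fracture, soft-tissue damage, or another elbow fracture or dislocation.
- Baseline blocks (Table 2): polytrauma is the only trauma item. It is zero for every patient after exclusion and so carries no information.
- Matching (Section 4.2): simple versus multi-fragmented, taken from the OPS code, is the one informative injury descriptor.
- Regression models (Section 4.2): no injury variable is named.
- Weighted analyses (Section 4.3): no covariate beyond the matching list is named.
- Bias discussion (Section 3.3): event timing and laterality are covered, injury severity is not. No quantitative analysis of unmeasured confounding is planned.

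No step closes the gap.

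**2. How large could the effect be?**

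For a binary severity marker with prevalence pL in LPF and pT in TBW that multiplies risk by R, with no true implant effect, the spurious LPF:TBW risk ratio is

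B = [1 + pL(R − 1)] / [1 + pT(R − 1)].

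All inputs are assumptions, and the prevalences must be those remaining **after** matching.

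- Combined elbow injury, pL = 20%, pT = 10%, R = 2: 1.20/1.10 = 1.09.
- The same prevalences with R = 3: 1.40/1.20 = 1.17.
- Open fracture, pL = 8%, pT = 4%, R = 3: 1.16/1.08 = 1.07.
- Wider range, low end, pL = 10%, pT = 5%, R = 1.5: 1.05/1.025 = 1.02.
- Wider range, high end, pL = 30%, pT = 10%, R = 3: 1.60/1.20 = 1.33.
- Equal prevalence, pL = pT: B = 1.00.

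If the imbalance runs the other way, the factors invert: 1/1.09 = 0.92 and 1/1.17 = 0.85.

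The consequence for testing depends on two more assumptions, the event risk and the matched sample size. Take a 20% TBW event risk and B = 1.095 (for example pL = 15%, pT = 5%, R = 2: 1.15/1.05). The LPF risk becomes 0.20 × 1.095 = 0.219. The chance of a false finding against LPF is then:

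- 3,000 per arm: 44% at two-sided 5%, and 20% at 0.05/6, the first Holm step for the six endpoints in Table 3.
- 1,000 per arm: 18% and 5.5%.

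**The case against.** The strongest objection is that confounding is supposed and not shown. The documents give no severity distribution by arm, and without imbalance there is no bias. If severity goes with multi-fragmentation, matching on complexity already removes part of any gap. This stands: the most that can be claimed is potential residual confounding. The Section 2.1 rule that sends same-day TBW-plus-LPF cases to LPF might suggest an imbalance, but the documents do not say that those patients are more severely injured.

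Three stronger readings are tempting and are not supported.

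- **Only polytrauma is removed.** Bilateral injury is excluded too, and the unclear-treatment criterion may take out some further patients.
- **Every TBW-LPF comparison is confounded.** The mechanism fits SC, revision and in-hospital complications. It is much less clear for implant removal alone, survival, length of stay or charges.
- **Planned second-stage surgery for an associated injury is scored as a complication.** SC procedures come from a closed code list and must be dated after the index operation. Whether staged repair of another elbow structure falls within that list needs the OPS catalogue, which the documents do not contain. Added covariates would not stop such procedures being counted in any case.

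A further fair objection concerns the remedy. Section 3.3 says ICD codes carry neither side nor order within a case, and Section 2.2 merges directly consecutive admissions into the index case. A dislocation diagnosis could therefore be a postoperative event, and luxation is itself an SC component. Careless use of such a code would adjust for an outcome. This does not defeat the point, but the fix has to guard against it.

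**Conclusion.** The gap in the covariate list is established from the text. No stated criterion removes open or combined elbow injuries, and fracture complexity is the only informative injury descriptor in any analysis. What follows is potential residual confounding, chiefly in the SC, revision and in-hospital complication comparisons.

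Its size and direction cannot be derived from the documents. A reader might take 1.07 to 1.17 as an estimate of the bias. It is an illustration that rests wholly on assumed post-matching prevalences and relative risks. Other plausible inputs give 1.02 to 1.33, or the inverse, or nothing at all. The false-finding rates rest in addition on an assumed event risk and sample size.

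The change is worth making before analysis because the diagnoses are already held. Even a finding that the indicators are balanced would strengthen the comparison.

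**What to change.** Add two index-case indicators to the Table 2 baseline block, with their ICD codes listed in advance:

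1. open fracture or soft-tissue injury;
2. concomitant elbow-region fracture or dislocation.

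Restrict both to acute-injury codes that Table 2 does not also use for complications. S51.86, for example, is already listed there as compartment syndrome. Where possible, take the codes from the admission containing the index surgery and not from later cases merged into the series. Include both indicators in the propensity score, the before-and-after balance table and the multivariable models. Because ICD codes have no order within a case, also run the models without the dislocation component.

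Add a sensitivity analysis of the primary endpoints, in each age study, restricted to patients with neither indicator. Re-match within that subset or re-check its balance. This analysis would also limit the influence of any staged procedures for associated injuries.

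The cost is two derived variables from existing data and several extra model runs, since there are several primary endpoints and two age studies. The restricted sample is smaller. Some misclassification will remain because side and sequence are missing; contralateral injuries, for instance, may be flagged. Section 3.3 already accepts the laterality limitation for osteonecrosis.

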4.3. Sensitivity analysis

As a sensitivity analysis, Cox regression analysis for OS, MAE, TE and SC as well as logistic regression analysis for 30-day mortality, IH-MAE, IH-TE and IH-SC will be also performed using the entire OF cohort with different weights:

Approach	Definition of weights	
	Control (LPF)	Treatment (TBW)
Entire cohort with original data*	1	1
Inverse Probability of Treatment Weighting (IPTW) ⁴	$\frac{1}{1 - p_s}$	$\frac{1}{p_s}$
Balanced (or overlap) weighting ⁵	p_s	$1 - p_s$

PS weighting ⁶	$\frac{\min(p_s, 1 - p_s)}{1 - p_s}$	$\frac{\min(p_s, 1 - p_s)}{p_s}$
---------------------------	--------------------------------------	----------------------------------

Table 5: Weighting approaches for sensitivity analysis. *As a first analysis, regression analyses will be performed using the entire cohort without weights. ^{4,5,6} refer to the references. p_s propensity score determined using logistic regression.

5. Treatment of Missing Values

Missing values or inconsistent data in sex, day of birth, exit date of database lead to exclusion from study. For all other variables, no missing data will occur in the study, since all variables will be defined by existing ICD/OPS or ATC codes. If no related code will be found, the according variable will be set to zero. Since the considered comorbidities are highly relevant for any reimbursement, it is very unlikely that they are not coded in the database. However, there could be a bias by setting all the variables as known variables.

6. Software

All statistical analyses will be performed using SAS (SAS Enterprise Guide Version 8.3, SAS Institute Inc., Cary, NC, USA) and R version 4.2.1, R foundation, Vienna, Austria.

References

3. Holm, S. (1979). A Simple Sequentially Rejective Multiple Test Procedure. *Scandinavian Journal of Statistics*, 6(2), 65–70.

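### The risk-factor aim has no analysis of its own: its main models sit in the matched set, and for surgical and minor outpatient complications section 4.2 names only subdistribution hazards

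*Combined protocol and SAP*

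**What the plan says.** The aim statement before section 2 gives two aims: the TBW versus LPF comparison, and "to identify independent risk factors for unfavorable course".

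Section 4.2 opens with the purpose "To analyze differences in the treatment groups (TBW versus LPF" and, for that purpose, states that "a 1:1 propensity score (PS) matching will be performed". It then fixes the population: "Analysis set will defined by all patients included in the matching". The regression models follow under that definition. For OS, MAE and TE, "Multivariable Cox regression models will analyze the impact of baseline variables on the endpoints". For SC and MOC, "death will be considered as a competing risk event", and the methods named are Aalen-Johansen incidence curves, Gray's test and "sub-distributional hazards using Fine & Gray Cox models", with HRs shown in forest plots. Section 4.2 names no cause-specific hazard model.

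Section 4.3 adds sensitivity analyses in the whole cohort: Cox regression for OS, MAE, TE and SC, and logistic regression for 30-day mortality, IH-MAE, IH-TE and IH-SC. According to the note to Table 5, the first of these "regression analyses will be performed using the entire cohort without weights". The section does not mention the risk-factor aim. It does not list revision, implant removal, IH-IAC, IH-non-IAC or MOC.

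**The concern.** Two features of the main analysis suit the treatment contrast better than the risk-factor aim.

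**Population.** Propensity matching balances TBW against LPF. It gives no protection against confounding of the effects of, say, dementia or osteoporosis on an outcome. Those effects rely on the regression model in either population. What matching does do is discard patients, so covariate effects are estimated less precisely for no gain on this aim.

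**Hazard scale.** A subdistribution HR combines a factor's effect on the complication with its effect on death. A factor that shortens life leaves less time in which a complication can occur, and so lowers the cumulative incidence even if it does not change the complication rate among survivors. Patients aged 70 and over are analysed and published separately, and the Table 2 covariates include dementia, heart failure, chronic kidney disease, cancer and care dependency. These plausibly raise mortality. In a forest plot labelled as risk factors, an HR below 1 for such a factor could be read as protection, and a true risk factor could be masked.

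**Working it through.** The documents give no sample size, arm sizes, event counts, matched fraction or mortality rates, so there is no planned figure to reproduce. All rates below are assumptions.

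**1. Which analysis covers which endpoint**

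| Endpoint | Full-cohort regression in 4.3? |
|---|---|
| SC, IH-SC (primary) | Yes, as sensitivity; type of Cox model for SC not stated |
| Revision, implant removal, IH-IAC, IH-non-IAC (primary) | No |
| OS, MAE, TE, 30-day mortality, IH-MAE, IH-TE | Yes, as sensitivity |
| MOC (secondary) | No |

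The unweighted full-cohort regression therefore covers two of the six primary endpoints in Table 3.

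**2. Precision lost by matching**

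With 1:1 matching without replacement (assumed), the largest share of the cohort that can be kept is f = 2 × the smaller arm's share: 60% if that arm is 30% of the cohort, 40% if it is 20%. If events fall in proportion, the standard error of a covariate effect rises by 1/√f:

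- f = 0.9: 1/√0.9 = 1.05
- f = 0.8: 1/√0.8 = 1.12
- f = 0.6: 1/√0.6 = 1.29
- f = 0.4: 1/√0.4 = 1.58

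For power, assume 600 events in the full cohort, a factor with 20% prevalence and HR 1.3. Schoenfeld's formula gives power = Φ(√(events × 0.2 × 0.8) × ln 1.3 − 1.96).

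- Full cohort: √96 × 0.2624 = 2.571; power 73%
- f = 0.9, 540 events: √86.4 × 0.2624 = 2.439; power 68%
- f = 0.6, 360 events: √57.6 × 0.2624 = 1.991; power 51%
- f = 0.4, 240 events: √38.4 × 0.2624 = 1.626; power 37%

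**3. Subdistribution HR for a factor with no effect on SC**

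Take a constant SC hazard s = 5% per year, baseline death hazard d, death HR h and T = 5 years. The cumulative incidence is

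CIF = s/(s + d) × [1 − exp(−(s + d)T)],

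with d replaced by h·d when the factor is present. The subdistribution HR is approximately ln(1 − CIF with factor) / ln(1 − CIF without).

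For d = 6% and h = 2:

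- Without the factor: 0.05/0.11 × (1 − e^−0.55) = 0.192, ln(1 − CIF) = −0.2136
- With the factor: 0.05/0.17 × (1 − e^−0.85) = 0.168, ln(1 − CIF) = −0.1844
- Ratio: 0.1844/0.2136 = 0.86

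The same formula gives 0.75 for d = 6%, h = 3, and 0.97 and 0.95 for d = 1% with h = 2 and 3.

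A simulation of 150,000 patients per scenario fitted both models with censoring at 5 years. It used the constant SC hazard and also an early-peaking one (25% per year for the first half-year, then 2%). The true cause-specific HR for SC was 1.0 or 1.2, and h was 2 or 3.

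| Baseline mortality | Fine-Gray HR, true 1.0 | Fine-Gray HR, true 1.2 |
|---|---|---|
| 1% per year | 0.95–0.99 | 1.14–1.17 |
| 6% per year | 0.78–0.94 | 0.87–1.12 |
| 10% per year | 0.67–0.92 | 0.82–1.08 |

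Where the truth was 1.0, cause-specific Cox returned 0.98 to 1.03. That spread shows the simulation error and accounts for the small gap between 0.75 by formula and 0.78 by simulation. With early-peaking SC at 6% mortality, the Fine-Gray HR was 0.94 (h = 2) and 0.89 (h = 3), so the effect is weaker when complications cluster soon after surgery.

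**The case against.** A reader might infer that risk factors are studied only in matched patients and that every risk-factor interval is wider than the data allow. The documents do not support that. Section 4.3 runs full-cohort regressions, including an unweighted one, for OS, MAE, TE, SC and four binary endpoints. For those eight the issue is which analysis is the main one. Nor does matching bias covariate effects in a correctly specified model; the loss is one of efficiency, and is small if 80% to 90% of patients are matched.

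A reader might also infer that Fine-Gray is the wrong model, or that markers of frailty will look protective. Neither follows. The introduction speaks of assessing a patient's expected complications in order to tailor treatment. That is prognosis in the presence of death, which subdistribution hazards describe. The term independent risk factor does not settle whether prognosis or aetiology is meant. The apparent protection is negligible at mortality plausible for patients under 70, and weaker if SC occur early. It is also partly visible from the planned OS model, where a factor that raises mortality should show an HR above 1. OS, MAE and TE count death as an event, so they are not affected. For SC, the Cox regression in section 4.3 might even be cause-specific, since its type is not given.

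All of this stands and limits the point. Three gaps remain: no analysis is named for the second aim, four primary endpoints and MOC have no full-cohort model, and no cause-specific model is stated for SC or MOC.

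**Conclusion.** The point holds as a gap in the plan, worth closing because it concerns a stated aim; it is not an error in the treatment comparison. Precision lost to matching ranges from slight (standard errors × 1.05 at 90% kept) to substantial (× 1.58 at 40% kept), and the documents do not show where in that range the study lies. The hazard-scale issue matters mainly for the study of patients aged 70 and over. There, under assumed mortality of 6% per year and a death HR of 2 to 3, a factor with no effect on SC shows an HR of about 0.78 to 0.94, and a true cause-specific HR of 1.2 can appear as 0.87 to 1.12. At 1% per year the first range is 0.95 to 0.99, which would not mislead anyone. These figures rest on assumed hazards and a five-year horizon; only the direction is independent of them.

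**What to change.** - In section 4.2, name the unweighted full-cohort multivariable regression (first row of Table 5) as the main analysis for the risk-factor aim.
- Extend it to revision, implant removal, IH-IAC, IH-non-IAC and MOC. Section 4.2 names no regression model for revision or implant removal, so state one, including how death is handled.
- State in section 4.3 whether Cox regression for SC means Fine-Gray or cause-specific Cox.
- For SC and MOC, report cause-specific HRs for the complication and for death beside the Fine-Gray results, and say that the former address aetiology and the latter absolute risk.
- Keep the matched set as the main analysis for TBW versus LPF.

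The Bonferroni-Holm adjustment covers only treatment-effect p-values, so it need not change. The claims data are already held. The cost is SAP wording, new full-cohort models for five endpoints, cause-specific models for SC, MOC and death, and a second HR column that needs explaining.
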